¹⁰ **All** concomitant medications/vaccinations and intercurrent medical conditions up to 1 month post Dose 2 of NTHi-MCat vaccine and **all** concomitant medications/vaccinations and intercurrent medical conditions associated with SAEs and pIMDs for the entire study period.

CONFIDENTIAL

209538 (NTHI MCAT-009)
Protocol Amendment 1 Final

¹¹. If a diagnosis of COVID-19 is made in accordance with the current WHO case definition, cases should be reported as AEs (unsolicited AEs, AEs leading to withdrawal) or SAEs (refer to Section 12.5 for safety definitions), and routine procedures for recording, evaluation, follow-up, and reporting of AEs, and SAEs should be followed in accordance with the time period set out in Table 15

¹². Visit may be a telephone contact, or other means of virtual contact or home visit during special circumstances (refer to Section 8.1 for information on study procedures during special circumstances)

Table 4 Schedule of Activities: NTHi-Mcat group (Amended 18 May 2020)

Epoch	Epoch 001								Epoch 002	
Type of contact	V1	C1	V2	V3	C2	V4	C3	C4	V5	C5
Time points	D1	D8	D31	D61	D68	D91	D241	D331	D421 ⁹	D661
Sampling time points	NM 1			NM 2						
Informed consent	●									
Check inclusion / exclusion criteria	●									
Collect demographic data	●									
Record previous vaccination data	●									
Measure record height and weight	●									
Physical examination ¹	●			0		0			0	
Smoking status	●									
Smoking exposure history (ATS-DLD-78A questionnaire)	●									
Vaccines										
Study group and treatment number allocation	●									
Treatment number allocation for subsequent doses ²	0			0						
Vaccine administration (NTHi-Mcat group) ³	●			●						
Recording of administered treatment number	●			●						
Clinical specimens for laboratory assays										
Blood sampling for antibody determination (~10 ml)	● ⁴					●				
Blood sampling for CMI response (~40 ml) ⁵	● ⁴					●				
Safety assessments										
Medical history	●									
Urine pregnancy test ⁶	●			●						
Check contraindications and warnings and precautions to vaccination	0			0						
Pre-vaccination body temperature	●			●						
Record any concomitant medication/vaccination ⁷	●	●	●	●	●	●	●	●	●	●
Record any intercurrent medical conditions ⁷	●	●	●	●	●	●	●	●	●	●

CONFIDENTIAL

209538 (NTHI MCAT-009)
Protocol Amendment 1 Final

Epoch	Epoch 001								Epoch 002	
Type of contact	V1	C1	V2	V3	C2	V4	C3	C4	V5	C5
Time points	D1	D8	D31	D61	D68	D91	D241	D331	D421 ⁹	D661

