⁸ **If a diagnosis of COVID-19 is made in accordance with the current WHO case definition, cases should be reported as AEs (AEs leading to withdrawal) or SAEs (refer to Section [12.5](#) for safety definitions), and routine procedures for recording, evaluation, follow-up, and reporting of AEs, and SAEs should be followed in accordance with the time period set out in [Table 15](#)**

⁹ **Visit may be a telephone contact, or other means of virtual contact or home visit during special circumstances (refer to Section [8.1](#) for information on study procedures during special circumstances)**

CONFIDENTIAL209538 (NTHI MCAT-009)
Protocol Amendment 1 Final

Whenever possible, the investigator should arrange study visits within the intervals described in [Table 5](#).

Table 5 Intervals between study visits

Treatment groups	Interval ^{1,2}		Optimal length of interval ³	Allowed interval
Sh_NTHi-Mcat_1 ¹	V1_1 (D1) →	V2_1 (D61)	60 days	60 – 80 days ⁴
	V2_1 (D61) →	V3_1 (D91)	30 days	30 – 50 days ⁴
	V3_1 (D91) →	C1_1 (D98)	7 days	7 – 11 days
	V3_1 (D91) →	V4_1 (D121)	30 days	30 – 45 days
	V3_1 (D91) →	V5_1 (D151)	60 days	60 – 75 days ⁴
	V5_1 (D151) →	C2_1 (D158)	7 days	7 – 11 days
	V5_1 (D151) →	V6_1 (D181)	30 days	30 – 45 days ⁴
	V5_1 (D151) →	C3_1 (D331)	180 days	180 – 210 days
	V5_1 (D151) →	V7_1 (D511)	360 days	360 – 390 days
	V5_1 (D151) →	C4_1 (D661)	510 days	510 – 540 days
Sh_NTHi-Mcat_3 ¹	V1_3 (D1) →	V2_3 (D61)	60 days	60 – 80 ⁴
	V2_3 (D61) →	V3_3 (D151)	90 days	90 – 110 days ⁴
	V3_3 (D151) →	C1_3 (D158)	7 days	7 – 11 days
	V3_3 (D151) →	V4_3 (D181)	30 days	30 – 45 days
	V3_3 (D151) →	V5_3 (D211)	60 days	60 – 75 days ⁴
	V5_3 (D211) →	C2_3 (D218)	7 days	7 – 11 days
	V5_3 (D211) →	V6_3 (D241)	30 days	30 – 45 days ⁴
	V5_3 (D211) →	C3_3 (D331)	120 days	120 – 150 days
	V5_3 (D211) →	C4_3 (D391)	180 days	180 – 210 days
	V5_3 (D211) →	V7_3 (D571)	360 days	360 – 390 days
Sh_NTHi-Mcat_6 ¹	V1_6 (D1) →	V2_6 (D61)	60 days	60 – 80 days ⁴
	V2_6 (D61) →	V3_6 (D241)	180 days	180 – 200 days ⁴
	V3_6 (D241) →	C1_6 (D248)	7 days	7 – 11 days
	V3_6 (D241) →	V4_6 (D271)	30 days	30 – 45 days
	V3_6 (D241) →	V5_6 (D301)	60 days	60 – 75 days ⁴
	V5_6 (D301) →	C2_6 (D308)	7 days	7 – 11 days
	V5_6 (D301) →	V6_6 (D331)	30 days	30 – 45 days ⁴
	V5_6 (D301) →	C3_6 (D481)	180 days	180 – 210 days
	V5_6 (D301) →	V7_6 (D661)	360 days	360 – 390 days

CONFIDENTIAL209538 (NTHI MCAT-009)
Protocol Amendment 1 Final

Treatment groups	Interval ^{1,2}		Optimal length of interval ³	Allowed interval

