8.5. Safety Assessments**(Amended 18 May 2020)**

The investigator and any designees are responsible for detecting, documenting, and reporting events that meet the definition of an AE or SAE.

Diagnosis of COVID-19 should be made in accordance with the WHO case definition. Cases should be categorised as AEs (unsolicited or AEs leading to withdrawal) or SAEs (refer to Section 12.5 for safety definitions), and routine procedures for recording, evaluation, follow-up, and reporting of AEs, and SAEs should be followed in accordance with the time period set out in Table 15 and Table 16.

The investigator and any designees remain responsible for following up AEs that are serious, considered related to the study treatment or the study, or that caused the subject to discontinue the NTHI MCAT-009 study.

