- Concerning the management of the Patient Informed Consent Forms, the following text is added:

The first copy of the Patient Informed Consent Form is kept by the investigator. The second copy is kept by the Medical Direction of GlaxoSmithKline France and the last copy(ies) is (are) given to the subject ~~and/or his/her legally authorized representative~~.

The second copy of all the consent forms will be collected by the Clinical Research Assistant (CRA) under ~~the's~~ the Investigator's control, and placed in a sealed envelope bearing only:

- the study number,
- the identification of the Centre: name of the principal investigator and centre number,
- the number of informed consents,
- the date,
- and the principal investigator's signature.

Then, the CRA hands the sealed envelope over to the Medical Direction, for confidential recording, under the responsibility of the Medical Director.

Overall Rationale for the Amendment 1 18 May 2020

This amendment is considered substantial based on the criteria defined in Article 10(a) of Directive 2001/20/EC of the European Parliament and the Council of the European Union because it significantly impacts the conduct or management of the trial.

The current analysis of the primary objective is planned on the per-protocol population. The use of the per protocol defined windows for vaccination and blood draws minimizes potential variability within the data for statistical comparisons. The planned analysis would test at least 1 geometric mean concentration (GMC) ratio (Sh_NTHi-Mcat over NTHi-Mcat) among anti-PD, anti-PE, anti-PilA, anti-UspA2 is inferior or equal to 0.667 in all time-lags under investigation at 1 month post-Dose 2 of NTHi-Mcat vaccine. To control the type I error below 2.5% (one-sided), a sequential procedure -is planned in the protocol. Starting from the 6-months lag, the 3-months NI will be tested only if the 6-months NI will be demonstrated, while the 1-month NI will be tested only if the 6-months and 3-months NI will be both demonstrated. The expected sample size would allow to reach 80% of power.

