The study started on 23 Apr 2019. At the time of writing, group Sh_NTHi-Mcat_1 and control group NTHi-Mcat have completed the vaccination schedule and the blood draw as dictated by the study protocol, whereas the less advanced groups (Sh_NTHi-Mcat_3 and Sh_NTHi-Mcat_6) are either due to receive the study vaccine or to undergo a blood draw. In accordance with the safety measures applied for COVID-19 containment in the Countries where the study is conducted, a number of study visits are unlikely to occur as

CONFIDENTIAL

209538 (NTHI MCAT-009)
Protocol Amendment 1 Final

planned. This is expected to impact 2 of the study groups (Sh_NTHi-Mcat_3 and Sh_NTHi-Mcat_6), for which the visits to collect data for primary endpoint are likely to occur while COVID-19 containment measures are in place.

This protocol amendment 1 includes a modified primary objective, should the Sh-NTHI-Mcat_6 **or** the Sh-NTHI-Mcat_3 and Sh_NTHi-Mcat_3 groups not meet the per-protocol defined sample size. To complement this modified primary analysis, a descriptive analysis where the 95% confidence intervals around the geometric mean concentration (GMC) ratio will be presented for any group not meeting the per protocol sample size using all available data. The descriptive analysis may be used to support the interval between *Shingrix* and NTHi-Mcat vaccines administration for the planned NTHi-Mcat Phase III studies.

This protocol amendment 1 also outlines measures (e.g. for safety monitoring) that may be applicable during special circumstances, like COVID-19 pandemic, in order to protect participant's welfare and safety, and as far as possible ensure the potential benefit to the participant and promote data integrity. However, if the study specific visit and procedures can be completed, then they should be completed according to the protocol, taking into account clinical judgment and local public health guidance to protect the safety of staff and subjects.

In addition, provisions relating to specific reporting of serious adverse events and serious adverse reactions, in accordance with Article R1123-54 and Article R1123-46 of the French Public Health Code, are incorporated into the "Requirements for France" Section of this Protocol Amendment, in order to fulfill the commitment taken with French Health Authority.

Amended text is indicated in ***bold italics*** in the body of the protocol.

Section # and Name	Description of Change	Brief Rationale

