Cover page	To swap the identifiers "short title" and "Detailed Title".	Identifiers need to be corrected
Contributing authors	Addition of new team members	To reflect changes in the Team and contributions to the protocol amendment
Sponsor signature page	To change the identifier "short title" to "Detailed Title".	The detailed title is presented on this page and the identifier needs to be corrected.
Investigator signature page	To change the identifier "short title" to "Detailed Title".	The detailed title is presented on this page and the identifier needs to be corrected.
Section 1 Synopsis; Objectives and endpoints	Modification of the primary objective in case the per-protocol sample size for 1 (or more) of the 4 study groups is not reached, including addition of footnote and update of subsequent footnote referencing.	To add a modified primary objective to be applied in case the per-protocol sample size for 1 (or more) of the 4 study groups is not reached. This is necessary because the current analysis of the primary objective is planned on the per-protocol population but, due to the containment measures for COVID-19 applied in the countries where the study is conducted, a number of

CONFIDENTIAL209538 (NTHI MCAT-009)
Protocol Amendment 1 Final

Section # and Name	Description of Change	Brief Rationale
		study visits are unlikely to occur as planned.
Section 2 Schedule of Activities (SoA) – Table 3 and Table 4	
Addition of footnotes:
 
 11 to add information related to the diagnosis of COVID-19 per the WHO case definition and to clarify that routine study procedures and timeframes for reporting of AEs / SAEs should be followed; and, 12 to add information regarding alternatives to study contacts due to special circumstances (e.g. COVID-19 pandemic) 	To provide a reference to the WHO case definition for COVID-19, and to clarify that recording of AEs (unsolicited AEs or AEs leading to withdrawal) or SAEs should be aligned with routine procedures for the detection, reporting and recording of AEs or SAEs and timeframes set out in the protocol. And, to add information regarding alternatives to study contacts due to special circumstances (e.g. COVID-19 pandemic)

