Secondary	
Within group assessment
 
The percentage of subjects with at least 1 local adverse event (AE) (solicited and unsolicited), with at least 1 general AE (solicited and unsolicited) and with any AE during the 7-days solicited follow-up period and the 30-days follow-up period will be tabulated by group with exact 95% CI after each NTHi-Mcat vaccine dose and overall. The percentage of NTHi-Mcat doses followed by at least 1 local AE (solicited and unsolicited), by at least 1 general AE (solicited and unsolicited) and by any AE will be tabulated by group with exact 95% CI. The same calculations will be performed for AEs rated as Grade 3, for AEs causally related to vaccination and Grade 3 AEs causally related to vaccination.
 
The percentage of subjects reporting each individual solicited local and general AE during the 7-days solicited follow-up period after each dose of NTHi-Mcat vaccine will be tabulated by group with exact 95% CI. The percentage of NTHi-Mcat doses followed by each individual solicited local and general AE will be tabulated by group with exact 95% CI.
 
Fever will be reported per 0.5°C cumulative increments.
 
For all solicited symptoms, the same tabulation will be performed for Grade 3 AEs.
 
The verbatim reports of unsolicited symptoms will be reviewed by a physician and the signs and symptoms will be coded according to the Medical Dictionary for Regulatory Activities (MedDRA) Dictionary for Adverse Event Terminology. The percentage of subjects with at least 1 report of unsolicited adverse event classified by the MedDRA and reported up to 30 days after NTHi-Mcat vaccinations will be tabulated by group with exact 95% CI. The same tabulation will be performed for Grade 3 unsolicited adverse events, for unsolicited adverse events with a causal relationship to vaccination and for Grade 3 AEs causally related to vaccination.
 
The number of subjects who experienced any serious adverse event (SAE) or any potential immune-mediated disease (pIMD) from Day 1 to Day 331 and from Day 331 to Day 661 will be reported.
 
The number of subjects who experienced any AE leading to study withdrawal, from first vaccination up to study conclusion, or any SAE related to study participation or concurrent GSK medication/vaccination, during the entire study period, will be reported.
 
A summary of subjects reporting concomitant medication/product will be provided.

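### The all-causality unsolicited, Grade 3 and combined AE rates by group have no version without COVID-19, although exposure of the 30-day windows to the pandemic probably rises with the lag after Shingrix

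*Protocol*

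**What the plan says.** **Recording.** The summary of changes in Protocol Appendix 8 gives the purpose of the new footnotes as "to clarify that recording of AEs (unsolicited AEs or AEs leading to withdrawal) or SAEs should be aligned with routine procedures". The rule in force is in the body of the protocol. For the Shingrix groups, Table 3 footnote 11 says "cases should be reported as AEs (unsolicited AEs, AEs leading to withdrawal) or SAEs", and the Table 15 footnote agrees. For the control group, Table 4 footnote 8 says "cases should be reported as AEs (AEs leading to withdrawal) or SAEs", and the Table 16 footnote agrees. Section 8.5, which refers to both Table 15 and Table 16, says "Cases should be categorised as AEs (unsolicited or AEs leading to withdrawal) or SAEs".

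**Timing.** Unsolicited AEs are collected for 30 days after each NTHi-Mcat dose (Protocol 5.2). Those doses fall on Days 1 and 61 in control, Days 91 and 151 in Sh_1, Days 151 and 211 in Sh_3, and Days 241 and 301 in Sh_6. The rationale for Amendment 1 states "The study started on 23 Apr 2019" and that, when it was written, "group Sh_NTHi-Mcat_1 and control group NTHi-Mcat have completed the vaccination schedule and the blood draw". It expects visits of the other two groups to fall under containment measures.

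**Analysis.** SAP Amendment 2, section 5.4.1, plans that unsolicited AEs by MedDRA classification and "reported up to 30 days after NTHi-Mcat vaccinations will be tabulated by group with exact 95% CI", with repeats for Grade 3, related, and Grade 3 related events. Sections 5.4.2.2 and 5.4.2.3 add stratification by causal relationship to NTHi-Mcat. COVID-19 appears in this SAP only in the list of abbreviations. Section 6 makes all comparisons other than the primary one descriptive.

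**The concern.** A stated secondary objective is the safety profile of NTHi-Mcat given 1, 3 or 6 months after Shingrix, or alone. All groups were randomised over the same months, but their AE windows are anchored to the NTHi-Mcat doses. The windows therefore sit in different calendar periods, and the shift follows the lag. An infection that began to circulate late in the study can add events to the long-lag groups and hardly any to control.

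In the all-causality totals this would have the same shape as an effect of prior Shingrix or of the interval. A MedDRA row for COVID-19 does not repair the totals. The same subject may have another unsolicited AE, so the row cannot be subtracted from the rate of subjects with any, any Grade 3 or any combined AE.

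**Working it through.** **1. Visit days.** Adding the optimal intervals in Protocol Table 5 reproduces the stated days:
- Sh_6: 1 + 60 + 180 = 241; + 60 = 301; + 30 = 331.
- Control: 1 + 60 = 61; + 30 = 91.
- Sh_1: 1 + 60 + 30 + 60 + 30 = 181.

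**2. Latest possible randomisation.** Sh_1 had completed its Day 181 blood draw when the amendment dated 18 May 2020 was written. The allowed intervals in Table 5 start at the optimal length, so Day 181 comes at least 180 days after randomisation. 18 May 2020 − 180 days = 20 November 2019. This is an upper bound; accrual may have ended earlier.

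**3. Latest control window day.** Day 90 is 89 days after randomisation: 20 November 2019 + 89 = 17 February 2020. At the widest allowed dose interval (75 days), with a window of the vaccination day plus 29 days: 20 November 2019 + 75 + 29 = 3 March 2020.

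**4. Sh_6 windows.** For a subject randomised on 23 April 2019, the first window opens on 19 December 2019 (+240 days) and the second closes on 17 March 2020 (+329). For a subject randomised on 20 November 2019 the same dates are 17 July and 14 October 2020.

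**5. Share of window days on or after onset.** The documents give no onset date and no accrual curve. Assumptions: flat accrual from 23 April 2019, last randomisation 21 September or 20 November 2019, nominal visit days, and 60 window days per subject. Each cell gives the result for the earlier and then the later end of accrual.

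| Assumed onset | Control | Sh_1 | Sh_3 | Sh_6 |
|---|---|---|---|---|
| 15 Feb 2020 | 0%, 0% | 6%, 23% | 32%, 51% | 86%, 90% |
| 1 Mar 2020 | 0%, 0% | 2%, 16% | 23%, 44% | 80%, 86% |
| 1 Apr 2020 | 0%, 0% | 0%, 8% | 11%, 30% | 61%, 72% |
| 18 May 2020 | 0%, 0% | 0%, 0% | 0%, 11% | 30%, 50% |

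With accrual weighted towards the start and onset on 1 April, Sh_6 falls to 41-54%. In no scenario does a shorter lag have a larger share than a longer one.

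**6. Effect on rates.** The documents give no incidence. Assume that 1-5% of subjects would have recorded COVID-19 over 60 fully exposed days. Excess = incidence × share exposed.
- Sh_6, low end: 1% × 0.61 = 0.6 percentage points; 0.0061 × 135 = 0.8 subjects.
- Sh_6, high end: 5% × 0.90 = 4.5 points; 0.045 × 135 = 6.1 subjects.
- Sh_3: from 1% × 0.11 = 0.1 to 5% × 0.51 = 2.6 points.
- Control: about 0.

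These are subjects with a COVID-19 event. The any-AE rate rises by less wherever such a subject already has another AE in the window. For scale, the exact 95% CI is 0-2.7% for 0/135 and 0.2-5.3% for 2/135.

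**The case against.** **The SAP already separates COVID-19 in part.** A reader might infer that it is never separated. That is too strong. Tabulation by MedDRA classification should make the terms visible by group, and the related-event tables should largely leave out an infection that the investigator judges unrelated. This objection stands. It leaves only the all-causality any, Grade 3 and combined rates.

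**The calendar facts are assumed.** A reader might also infer that control windows closed before the pandemic, or that most Sh_6 window days fell in it. The documents establish neither. They bound the control windows and say that later visits are expected under containment measures, but date no onset. Most fails for Sh_6 if onset is put at the amendment date (30-50%). Missed or delayed doses also make nominal days approximate, and SAP 4.2.5.1.1 drops a subject from the unsolicited set at a visit without a dose. The direction survives; the exact shares do not.

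**The control footnote proves little.** Its silence on unsolicited AEs fits windows that had already closed, but no reason is given. Section 8.5 names unsolicited AEs for both tables, and footnote 11 names them for Sh_1, which had also finished dosing. The point does not need this inference.

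**The effect is small and the endpoint descriptive.** True: no test or success criterion changes.

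**Removing COVID-19 can mislead too.** Containment may have reduced other infections, and Protocol 8.1 allows remote safety contacts. Rates without COVID-19 could then be too low at long lags. This also stands, and it determines how the extra tables should be used.

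**Conclusion.** The point holds in a limited form. Followed as written, SAP 5.4.1, 5.4.2.2 and 5.4.2.3 give all-causality any, Grade 3 and combined AE rates by group that include COVID-19 and have no counterpart without it. The exposure behind this is probably ordered by lag: about 0% of window days in control, 0-23% in Sh_1, 11-51% in Sh_3 and 61-90% in Sh_6 under flat accrual and onset between 15 February and 1 April 2020. At an assumed 1-5% incidence per 60 exposed days, that is about 1-6 of 135 Sh_6 subjects with a COVID-19 event.

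The bound on the control windows comes from the documents; onset, accrual shape and incidence are assumptions. The consequence is a modest distortion of a descriptive safety comparison, not a changed conclusion on the primary objective.

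It does not follow that the rates without COVID-19 are the correct lag comparison, because other calendar effects remain in them. Nor does the point extend to the SAE and pIMD tables anchored at Day 1: those cover the same study days in groups randomised over the same months. The SAE tables anchored to the NTHi-Mcat doses are limited to related events.

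**What to change.** In SAP 5.4.2.2 and 5.4.2.3:
- Repeat the all-causality any, Grade 3 and combined AE summaries by group without COVID-19 terms, using a MedDRA term list fixed in advance that matches the study's case definition.
- Present these beside the planned versions.
- Show by group the share of 30-day window days that fell under containment measures, from actual dose dates and stated calendar dates.
- State that neither version alone is the comparison between lags, because fewer other infections and remote safety contacts may also have changed the rates.

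Leave the Day-1-anchored SAE and pIMD tables as they are. The cost is a few extra tables from AE data already collected, plus a decision on which dates count as containment. The remaining drawback is that the tables show one calendar effect and do not correct for the others.
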